2.2 Setting

Formative phase

All interviews will be conducted in a *private* setting identified either by the researcher or the key stakeholder (i.e., personal office). The researcher will arrange a private office in a convenient location for the interview to be conducted.

Intervention Development Phase

The investigative team and the advisory board will work together to develop the pharmacy PrEP delivery model.

Transitional Pilot Phase

The transitional pilot phase will take place in two pharmacies that are located in high poverty and racial minority neighborhoods. We will provide pharmacy staff participants with flyers to disseminate to their pharmacy clients to take an eligibility screener and social and behavioral survey. Posters advertising the survey will also be placed throughout the pharmacy in case any client participants who visit the pharmacy in-person are interested.

Pharmacy staff participants will complete a short orientation to learn the study activities. The study activities are as follows: place study flyers in client participants' medication delivery packages; hang posters in their pharmacies about the study; and direct any questions that client participants may have about the study to our research team. Given that the study will ask sensitive questions about HIV and PrEP, pharmacy staff participants will receive two Continuing Education (CE) credit by participating in a training on understanding HIV in the community and mobilizing community pharmacies to improve access to PrEP. The orientation and training will take place online on Zoom.

Pharmacy staff participants will participate in a one-hour phone interview at baseline and 3-month of the intervention.

Pharmacy client participants who are made aware of the study by the pharmacy staff participants, and are interested will take a 3-minute eligibility screener. Eligible participants will then be prompted to complete a 20-minute social and behavioral survey. The screener and survey will be administered online using links for Survey Gizmo. The screener and survey, similar to self-administered online surveys, will not require the presence of the research or pharmacy staff. During the survey, we will inquire about sensitive subjects (mental, sexual and behavioral health). If needed, pharmacy client participants may be offered linkages to community services to meet their healthcare needs. Pharmacy client participants may refuse to participate in the study or to receive additional referrals at any time.

Pilot Phase

The pilot phase will take place in two pharmacies that are located in high poverty and racial minority neighborhoods. All pharmacies will have a large, private space where client participants/patients who agree to be screened and linked to PrEP can have privacy. If necessary, we will provide additional wall partitions/ screens, noise machines and noise-cancelling curtains to enhance privacy.

Pharmacy staff participants will complete a thorough training via the Canvas platform to learn the study activities. Our Canvas site will link trainees to privately posted YouTube videos that contain training material. Additionally, pharmacy staff participants will complete a module in HIV Prevention and Counseling. During training, pharmacy members will complete a pre-post survey about HIV Care and Prevention using Alchemer software. These trainings will take place virtually.

Pharmacy staff participants will participate in a one-hour interview at baseline, 3-month and 6-month of the intervention. These interviews will take place in a private office in the pharmacy.

Pharmacy client participants who are recruited into the pilot study will complete a 20-minute social and behavioral screener using Alchemer on an easy to use, touch screen tablet in a private room in the pharmacy. *Trained pharmacy staff will set up these interviews in the private area of the pharmacy but will not administer the survey.* In the event that a participant has a physical or intellectual disability that renders them unable to use the tablet, a study team member will orally administer the survey. The screening survey, similar to the self-administered online surveys, will not require the presence of the research or pharmacy staff participants outside of them showing them to the tablet in a private room. Potential pharmacy client participants may complete the screener using the QR code found on recruitment flyers, complete it on study iPads if recruited by staff, or (if needed) be screened orally by a team member. If eligible, pharmacy client participants may be offered a free HIV test. If pharmacy client participants accept, then the HIV test will be completed in the same private area of the pharmacy. Pharmacy client participants may refuse to participate at any time or if they have time constraints, they can schedule the test at a later date. If they are uncomfortable completing the screening in the pharmacy, we will also provide them with a referral for a PrEP prescribing physician.

2.3 Recruitment and enrollment

Formative Phase

To enroll *pharmacists* (n=10) and *technicians* (n=10), we will identify all pharmacies in the highest HIV zip code in Atlanta as shown by AIDSVu. AIDSVu is an online, interactive display of HIV prevalence across the US. Using an existing list of all pharmacies in the state of Georgia obtained from the Georgia Board of Pharmacy, we will generate a list of pharmacies from high HIV zip codes and then randomly contact each pharmacy to determine whether pharmacists or technicians are interested in participating in the study. Preliminary studies have indicated a sampling frame of about 43 pharmacies.

To enroll *PrEP prescribing physicians* (n=10) we will randomly select, and call physicians located in (or near) high HIV zip codes in Atlanta who have registered with PrEP locator (PrEPlocator.com). PrEP locator is an online, Emory maintained database of physicians who offer PrEP across the US, which was developed by co-investigator (co-I) [name].

To enroll *BMSM* we will rely on referral of the population by NAESM, our community partners. NAESM hosts large HIV testing drives at sites frequented by BMSM (i.e., bars, clubs' college events). They will inform men of our study and will schedule interviews with interested men at pre-specified dates on our

behalf.

Intervention Development Phase

The investigative team and advisory board are identified on this IRB protocol. These are experts in HIV prevention, rather than study participants. Thus, no recruitment will occur during this phase.

Transitional Pilot Phase

To enroll pharmacies, we will choose two pharmacies located in high poverty, racial minority neighborhoods will be selected from a sampling frame of about 43 pharmacies. In order for the pharmacy to participate, consent will have to be obtained from at least 1 pharmacist participant and 2-3 technician participants (n=4 per pharmacy).

To enroll pharmacy client participants, trained pharmacy staff will discreetly place flyers in clients' medication delivery packages to inform men about the eligibility screener and the social and behavioral survey. Pharmacy client participants will be directed online where they can privately consent to the study and complete the screener and survey. Pharmacy client participants who complete the eligibility screener will receive a \$1 pharmacy coupon regardless of their eligibility or willingness to participate in our study. Eligible pharmacy client participants who are willing to complete the social and behavioral survey will be compensated \$25 for their time. Pharmacy client participants will be informed during the informed consent process that the information they provide will be used to determine their HIV risk, and they may be offered referrals for STIs/HIV testing and PrEP.

Pilot Phase

To enroll pharmacies, we will choose two pharmacies to pilot test the pharmacy PrEP delivery model. Pharmacies that are located in high poverty, racial minority neighborhoods will be selected from a sampling frame of about 43 pharmacies. In order for the pharmacy to participate, consent will have to be obtained from at least 1 pharmacist participant and 2-3 technician participants (n=4 per pharmacy).

Pharmacy staff participants will discreetly inform their pharmacy clients about the study. If the pharmacy client is interested and willing to learn more about the study, the pharmacy staff participant will direct them to an area where they can privately provide electronic informed consent and complete the electronic screener. If they are unwilling or do not have time, they will be encouraged to return to the pharmacy when they have time. Pharmacy client participants who agree to complete the social and behavioral screener will be compensated \$25 for their time regardless of their eligibility or interest in being clinically screened for PrEP. Participants will be informed during the informed consent process that the information they provide will be used to determine their HIV risk and they may be offered a free HIV test.

2.4 Procedures

Formative Phase

Procedures for qualitative in-depth interviews

1. Initial contact and invitation to participate in an in-depth interview about PrEP screening and referral in pharmacies for MSM will be performed over the phone.
2. An appointment will be made with individuals who are willing to participate in the interview.
3. We will conduct individual in-depth qualitative interviews with two different kinds of key informants: **1) interactor participants** (pharmacists, technicians and PrEP prescribing

physicians) who interact with BMSM on a day to day basis and will be able to provide information about how the pharmacy and medical systems works at a practical level; and 2) **BMSM participants** who will describe their interactions with and perceptions of pharmacists and PrEP prescribing physicians, their receptiveness to pharmacy-based interventions, as well as their interactions with and attitudes towards the legal, public health and HIV prevention and care systems.

4. The interview process will be semi-structured and the interview guide will be targeted to the type of key informant. Topic guides will be used to guide the interview.
5. Qualitative data collection will assess barriers and facilitators of pharmacy PrEP delivery and discuss ways to support a sustainable pharmacy PrEP delivery model. Moreover, with each participant, we will describe the preliminary PrEP model for specific feedback on each step with respect to advertising, recruitment of BMSM, costs and other concerns. The interviews will also cover a range of topics within four domains: general public health and HIV/AIDS policy, pharmacy utilization of health services, pharmacy-based HIV prevention services including PREP, and pharmacy-physician partnerships. Specific questions will address: support for PREP screening, policies influencing PrEP delivery, referral and monitoring in pharmacies, potential barriers to the delivery of an intervention in a pharmacy, knowledge of epidemiologic data on HIV, sexual behavior, drug use and PREP, and sustainability through pharmacy-physician collaboration.
6. All interviews will be recorded for transcription and data analysis.
7. Interview recordings and paper notes will be stored in a locked cabinet in a lock office.
8. All of the data (transcripts) and analysis related to this study will be stored on network drives only available to the investigator and research assistant. The data will be anonymized, and the identity of the participants will be kept in a separate network drive, only available to the study investigator.

Procedures for workflow assessments

1. Direct observation of the pharmacy (for pharmacists and technicians) or physician office (for PrEP prescribing physicians) will be performed to understand routine and non-routine activities⁴⁴.

For *pharmacists and technicians*, the research assistant will focus on the door-to-door patient experience of obtaining a prescription as well as the process implemented behind the counter for filling a prescription. We will also pay particular attention to the pharmacist and technician procedures for patients obtaining a primary prevention service such as an immunization in the pharmacy. We will take note of the procedures performed to prepare for the immunization (i.e., authorization calls, collection of all materials, privacy partition set up) and following the administration of the immunization (i.e., logging of service performed, department of health reporting) including the time taken to perform each of these procedures.

For *PrEP-prescribing physicians*, researchers will focus the workflow assessment on the administrative process performed before and after seeing patients. In consideration of patient privacy, research assistants **will not sit in on patient visits**. Rather they will shadow the physicians once a patient visit is complete to understand how patient prescriptions are filled and how interaction occurs between the pharmacist and physician.

2. Research assistants will monitor the day-to-day procedures in each environment during a morning or afternoon work shift; whichever is most convenient for the participant. Observations will be made from a non-intrusive area. As time allows, open-ended questions will be asked to clarify observations.
3. Workflow diagrams for the pharmacy and physician offices will be created and patterns will be

examined across each environment to create an overall description that best represents a typical prescribing encounter⁴⁴.

Intervention Development Phase

1. The investigative team will review and analyze the data from the qualitative interviews and work-flow assessment.
2. All of the data will be reviewed, summarized and shared with the advisory board to assist with the development of the pharmacy PrEP delivery model.
3. The investigative team will develop 2-3 simulations of the potential pharmacy PrEP delivery model and present those step-by-step to the advisory board.
4. The advisory board will provide feedback on the study protocol, pharmacy trainings, pharmacy recruitment brochure, survey instruments and other materials as needed.
5. Using the adaptive protocol method, we will iteratively revise the protocol over the course of the study to ensure its feasibility, acceptability, and safety^{45,46}.
6. We will debrief about the study activities **every month** of the pilot study to refine the protocol for immediate implementation in the study activities.
7. Proposed changes will be assigned to subject matter experts from the co-I's on the grant.
8. Subject matter expert and other co-Investigators will vote on whether the change will be made immediately, revoked or followed through the next monthly meeting.
9. Agreed upon changes will be submitted to the IRB for approval.
10. Meticulous records of the development and revision process of the pharmacy PrEP delivery model will be kept throughout the study.

Transitional Pilot Phase

Pharmacy eligibility, enrollment and data collection

1. Two pharmacies that are located in high poverty, racial minority neighborhoods will be chosen to evaluate eligibility and willingness of BMSM to receive PrEP in pharmacies.
2. We will obtain consent from at least 1 pharmacist and 2-3 technicians at each pharmacy to participate in the study.
3. Pharmacy staff participants will earn 2 CE credit at an online Pharmacy Training Seminar to teach them how to mobilize community pharmacies to improve PrEP access.
4. Pharmacy staff participants will also participate in a short orientation to learn the study activities. The study activities are as follows: place study flyers in pharmacy client participants' medication delivery packages; hang posters in their pharmacies about the study; and answer any questions that client participants may have about the study.
5. Research staff will provide each pharmacy with flyers, posters, and information in case client participants need to be referred to third-party organizations for health services.
6. One-hour in-depth interviews will be administered to pharmacy staff participants at baseline and 3-month of the transitional pilot study.
7. Pharmacy client participants will receive information about the study from flyers or pharmacy posters.
 - a. Pharmacy client participants will use the QR code on the flyers or posters to access the eligibility screener.
 - b. After taking the screener, eligible pharmacy client participants will be prompted to take the social and behavioral survey.
 - c. Pharmacy client participants will receive electronic compensation at the end of the eligibility screener and/or social and behavioral screener.

Pilot Phase

Pharmacy eligibility, enrollment and data collection

8. Two pharmacies that are located in high poverty, racial minority neighborhood will be chosen to pilot test the pharmacy PrEP delivery model.
 - a. All pharmacies will have a large, private space where pharmacy clients who agree to be screened and linked to PrEP can have privacy. If necessary, we will provide additional wall partitions/ screens, noise machines and noise-cancelling curtains to enhance privacy.
9. We will obtain informed consent from at least 1 pharmacist and 2-3 technicians at each pharmacy to participate in the study.
10. Pharmacy staff participants will participate in a virtual Pharmacy Training Seminar that will take approximately 1.5 hours to complete. The training will follow the guidelines of the Pharmacy Staff Training Manual for all participating pharmacies.
11. During the virtual Pharmacy Training Course, pharmacy staff participants will participate in a HIV Prevention and Counseling module to learn post-test HIV counseling.
12. One-hour in-depth interviews will be administered to pharmacy staff participants at baseline, 3-month and 6-month of the pilot study.

Pharmacy training seminars

1. The objective of the pharmacy training seminar is to equip participating pharmacy staff with the tools needed for optimal PrEP delivery. *While pharmacy staff participants will not be required to provide care to pharmacy client participants, our goal is to assess pharmacy staff participants increase in HIV knowledge over time.*
2. The investigators will provide pharmacy staff participants with a training manual to help pharmacy staff participants understand the specific challenges of the BMSM population with respect to HIV prevention and PrEP. The sections of the training manual will be as follows: pharmacy staff as public health providers, the scope of the problem with HIV in the community, understanding cultural challenges and barriers of BMSM, research ethics, patient eligibility for PrEP, PrEP payment options, training services that will be offered in the pharmacy (i.e. PrEP delivery, HIV testing), the importance of PrEP in HIV prevention, PrEP safety, the availability of PrEP locally in the community and relevant contact information, and other PrEP and HIV services available in the community that may be important to know about (e.g., medical/healthcare services, prevention, mental health services, support groups for HIV positives, etc.).
3. Research assistants will undergo extensive training to ensure standardization of the pharmacy training protocol in both pharmacies.
 - a. Research staff will practice role-playing strategies to suggest various techniques for engaging client participants.
4. Pharmacy staff participants will receive virtual training via Canvas and walk-through the intervention activities including engaging client participants, providing the social and behavioral survey, offering the biological screening kit, interpreting the results and linking to PrEP.
5. Pharmacy staff participants will be required to complete a HIV Prevention and Counseling module through the virtual Canvas training course to equip them with HIV counseling concepts, basic counseling skills, HIV prevention counseling and how to conduct the six-step HIV prevention counseling protocol.

Pharmacy-based PrEP delivery

1. Pharmacist participants will be asked to stock generic PrEP medication to ensure that eligible

participants are provided with 30-days of PrEP medication. Pharmacies will be compensated by the research team for the cost of the medication and receive a \$50 dispensing fee for each prescription dispensed.

2. Pharmacy staff participants will provide a pharmacy brochure highlighting that they offer pharmacy PrEP delivery tailored to the Atlanta area and for those who patronize the pharmacy. Pharmacy posters normalizing PrEP and HIV will be carefully tailored to the community of the pharmacy. These posters will be designed to appeal to the general customer base and be placed inside and outside of the pharmacy. These posters will be placed with other health literature to avoid singling out HIV-related services that may inadvertently add stigma.
3. Pharmacy staff participants will discreetly inform pharmacy clients (n=60) about the study. Pharmacy clients who are interest and willing will complete an electronic eligibility screener.
 - a. *In cases of long lines in the pharmacy and privacy is not possible, we will discourage pharmacy staff from delivering detailed information (at this particular visit) to protect anonymity of their customer; this will be done consistently across each pharmacy.*
4. Pharmacy client participants who agree to participate will be directed to an area where they can privately provide electronic informed consent and complete the eligibility screener. They will be informed at the end of the survey if they are eligible for the 20-minute social and behavioral survey via an electronic prompt. Eligible pharmacy client participants can immediately complete the social and behavioral survey or return to the pharmacy at a later time to do so. and their customer visit will be logged.
5. The consent form and survey will be self-administered via an electronic tablet so it will NOT require the presence of the pharmacy staff participants outside of them directing them to the private room where the tablet is set up. To circumvent potential literacy issues, the participant will listen to questions via headphones and mark their answers using the touch screen computer. If the participant has a physical or mental condition that renders them unable to use the tablet, the survey will be administered orally by a study team member. Audio recordings of the questions will be utilized throughout Alchamer wherever possible in case of literacy barriers.
 - a. The electronic survey platform, Alchamer, will allow us to automatically identify individuals who are behaviorally appropriate for PrEP. A password-protected document will be automatically generated to inform the pharmacy staff participants if the individual is eligible for the clinical PrEP screening. The pharmacy staff participants will not know what behaviors were reported by the pharmacy client participant to deem eligibility. They will just have an affirmative or non-affirmative response that indicates the pharmacy client participants eligibility.
 - b. Pharmacy client participants who complete the eligibility screener will receive \$1 and \$25 for the social and behavioral survey regardless of their eligibility or interest in being clinically screened for PrEP.
6. The pharmacy client participants will inform the pharmacy client participant if they are eligible to participate in the clinical screener.
7. Pharmacy client participants who are eligible and agree to the HIV test will be provided with a pre-packaged kit of a self-administered test for HIV and directed back to the private area of the pharmacy to perform their screenings. A recent “PrEP-at-home” pilot study conducted by co-I [name] showed high levels of comfort and efficacy of MSM self-administering HIV tests at home without supervision⁴⁷.

- a. Video and visual instructions will be provided on the tablet and paper to guide pharmacy client participants through the process of each test. Pharmacy client participants will also be able to reach an Emory staff member via phone or videoconference for questions about specimen collection.
 - b. We expect that 90% of pharmacy client participants will be able to complete these tests in a private area⁴⁷. Our community partners at NAESM also conduct self-testing at their community center and have high levels of participation.
4. We will ask pharmacy client participants who decline to be screened for PrEP to complete a 1-2-minute survey to explain their reasoning for declining the HIV test.
8. Pharmacy client participants will be asked to return the screening tests to the pharmacy staff participants. While their tests are being processed, we will ask them to complete an electronic post clinical screener survey that collects their follow-up information (phone number, email, address and contact for someone who can reach them) and ascertains their experience performing the self-screening tests in the private area.
 - a. They will be assured that we will only use this information to follow-up with them about the study and their information nor personal data will be shared with anyone other than themselves.
9. The pharmacy staff participants will process/ interpret the results of the rapid HIV test first in case a treatment referral needs to be set up.
10. Pharmacy client participants who test HIV negative will be provided with their results and be given a 30-day prescription for PrEP, culturally appropriate PrEP counseling and a follow-up appointment with co-I [name] or another PrEP prescribing physician identified through PrEPlocator.org, whichever is closest.
 - a. A PrEP prescribing physician will be available via phone during the testing process to provide participants with a prescription of 30-day PrEP.
 - b. We will inform the individual that a 30-day PrEP prescription will be required to achieve protection from HIV but in order to sustain protection, they need to continue PrEP beyond the 30-day period.
11. Pharmacy client participants may refuse to participate at any time or if they have time constraints, they can schedule the clinical screening at a later date. If they are uncomfortable completing the screening in the pharmacy, we will also provide them with a referral for a PrEP prescribing physician.
12. Pharmacy client participants who test HIV positive will receive post-test counseling from the pharmacy staff, who underwent intensive post-test counseling. Pharmacy client participants will be immediately sent for confirmatory testing and linkage to treatment at our community partner (NAESM) or co-I [name].
 - a. If needed, we will provide transportation for those who test positive to the clinic (if physically open pending COVID-19) and a research assistant from Emory or NAESM will be available to accompany the participant.
13. Pharmacy client participants who have an inconclusive HIV test will be told that their test is inconclusive and will be referred to our community partner, NAESM, for a confirmatory HIV test.
14. Once the pharmacy client participant completes the study activities they will be thanked for their time. In case of inclement weather, a research team member will offer to order an Uber or Lyft for the participants.

15. We will complete a 3-month follow-up phone call with pharmacy client participants who have test for HIV to assess linkages to PrEP/HIV care.

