In the transitional pilot phase, two pharmacies will be chosen to estimate how many pharmacy client participants would be eligible for the pilot phase. Among those who would be eligible, we will assess their willingness to receive PrEP in pharmacies. In order to recruit a sample of pharmacy client participants, pharmacy staff participants will place flyers in pharmacy client participants' medication delivery packages and hang posters in their pharmacies. Given the COVID19 pandemic, many client participants are opting for medication delivery versus in-person pick up. The flyers and posters will contain information about the pharmacy-based PrEP delivery study. A QR code will allow client participants to be directly linked to the eligibility screener. After taking the eligibility screener, client participants will be eligible for the social and behavioral survey if they are: 1) male or trans male, 2) had any types of sex in the past 6 months, 3) engaged in unprotected sex in the past 6 months, 4) had protected and/or unprotected sex with HIV positive partners in the past 6 months, and 4) injected any drugs in the past 6 months. We will ask pharmacy staff to insert flyers into patient medication deliveries over a 3-month period and during this time we will assess pharmacy staff barriers and facilitators of engaging with client participants regarding the study.

In the pilot test phase, two pharmacies will be chosen to pilot test the pharmacy PrEP delivery model. We will recruit pharmacy staff participants who work in each pharmacy and pharmacy client participants that patronize these pharmacies. Pharmacy staff participants will complete a pharmacy-based HIV prevention training to equip them with the tools needed for optimal PrEP delivery. Since the pharmacies selected to be a part of the study are located in racial minority neighborhoods, we anticipate that most client participants will be racial minorities. We will be collecting both qualitative and quantitative data to assess the impact of the pharmacy PrEP intervention on the pharmacy environment, personnel, and business flow. Among the pharmacy client participants, we will assess feasibility, acceptability and safety of the intervention activities, satisfaction with the activities and participation in activities without stigmatization, discomfort, or harm.

Pharmacy client participants will be considered eligible for the social behavioral survey if they:

- Consent to participate in the online screener

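### Clients who accept a self-test kit and stop without returning a test have no stated measure of their experience, so a completer-only comfort figure could be up to 10 points too high if about 10% do not complete

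*Combined protocol and SAP*

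**What the plan says.** Section 2.1 (pilot test phase) undertakes to assess, among pharmacy clients, feasibility, acceptability, safety, satisfaction and "participation in activities without stigmatization, discomfort, or harm".

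Section 2.4 (Pilot Phase, Pharmacy-based PrEP delivery) sets the steps around the self-test:

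- **Item 7b:** "We expect that 90% of pharmacy client participants will be able to complete these tests in a private area".
- **Unnumbered in sequence, between items 7b and 8:** a short survey for clients "who decline to be screened for PrEP to complete a 1-2-minute survey to explain their reasoning for declining the HIV test".
- **Item 8:** "Pharmacy client participants will be asked to return the screening tests to the pharmacy staff participants". Then: "While their tests are being processed, we will ask them to complete an electronic post clinical screener survey". This survey takes follow-up contact details and "ascertains their experience performing the self-screening tests in the private area".
- **Item 11:** clients may refuse at any time or reschedule. "If they are uncomfortable completing the screening in the pharmacy, we will also provide them with a referral for a PrEP prescribing physician".
- **Item 15:** the 3-month call goes to clients who tested and asks about linkage to PrEP or HIV care.

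Section 2.11 (Pharmacy client participant data) plans exploratory proportions for feasibility, acceptance, safety and PrEP use. It gives no denominator and no rule for clients who start the self-test and do not finish.

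**The concern.** The only client instrument that asks about the self-testing experience is timed to the processing of a returned test. Discomfort is a plausible reason to stop. Being asked about discomfort may therefore depend on not having stopped because of it.

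Aim 3 is about feasibility, acceptability and safety, and section 2.9 says the results will inform a future efficacy trial. Clients who took a kit and gave up could say most about what needs changing in the room, the kit or the instructions. A comfort proportion built from item 8 alone would describe those who got through, yet could be read as describing everyone who agreed to test.

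**Working it through.** **Which stated step reaches a client who accepts a kit, stops and returns nothing?**

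| Step (section 2.4) | Whom it covers | Does it ask about the experience? |
|---|---|---|
| Decline survey, between 7b and 8 | Decliners; clients who stop are not mentioned | No, reasons only |
| Item 8 survey | Clients whose returned tests are being processed | Yes |
| Item 11 | Clients uncomfortable testing in the pharmacy | No, referral only |
| Item 15 call | Clients who tested | No, linkage only |

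Follow-up contact details are collected in the item 8 survey itself, so the plan states no later route to a client who misses it.

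**The plan's own figure.** The 90% is an expectation taken from a cited study and cannot be rebuilt from the documents. Its complement is 1 − 0.90 = 0.10. Treating this as the share of kit recipients who do not complete is an assumption.

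**Formula.** Let pC and pN be the shares comfortable among completers and non-completers.

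- All-recipient comfort = 0.90·pC + 0.10·pN
- Overstatement = pC − (0.90·pC + 0.10·pN) = 0.10·(pC − pN)

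Both pC and pN are assumptions. Overstatement in percentage points:

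| pC | pN = 0 | pN = 50% | pN = pC |
|---|---|---|---|
| 100% | 10 | 5 | 0 |
| 90% | 9 | 4 | 0 |
| 80% | 8 | 3 | 0 |
| 70% | 7 | 2 | 0 |

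The ceiling is 10 points, the assumed share of non-completers.

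**Against sampling error.** The number of kits is not stated. Section 2.4 item 3 gives 60 as the number of clients informed about the study, so 60 is an upper limit. With about 90% of completers comfortable, no non-completer comfortable, and exact (Clopper-Pearson) 95% intervals:

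| Kits | Non-completers | Completers only (95% CI) | All recipients | Shift |
|---|---|---|---|---|
| 60 | 6 | 49/54 = 90.7% (79.7% to 96.9%) | 49/60 = 81.7% | 9.1 |
| 40 | 4 | 32/36 = 88.9% (73.9% to 96.9%) | 32/40 = 80.0% | 8.9 |
| 20 | 2 | 16/18 = 88.9% (65.3% to 98.6%) | 16/20 = 80.0% | 8.9 |

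At 60 kits the worst-case shift is about the half-width of the interval, (96.9 − 79.7)/2 = 8.6 points, and the all-recipient figure lies just inside it. At 20 kits it lies well inside.

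**The case against.** Four stronger readings are tempting, and the documents do not support them.

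- **That only a finished test triggers the survey.** Item 8 speaks of returning the tests. A partial or failed test could be handed back, and item 13 provides for inconclusive results. The gap concerns clients who return nothing.
- **That clients who stop are never asked anything.** The decline survey is listed after kit hand-out, and item 11 allows refusal at any time. Staff could reasonably treat stopping as declining, and the client might then name discomfort as the reason. But the plan does not say so, and a reason is not a rating of the experience.
- **That 10% of kit recipients will stop, from discomfort.** Item 7b does not define its denominator, does not say that the remainder start and stop, and gives no cause. Some may reschedule under item 11, complete later and then meet the item 8 survey.
- **That comfort and acceptability are overstated.** This requires non-completers to be less comfortable and the analysis to use completers only. Section 2.11 fixes no denominator. Section 2.1 describes acceptability more broadly than this one survey, and the survey instruments are not in the documents.

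It can also be said that non-completion is countable from kits given and tests returned. Monthly debriefs, bi-weekly check-ins, staff interviews and the help line in item 7a may bring problems to light, and adverse events are reported separately (2.7, 2.8). So feasibility and safety information is not lost through this gap. None of these routes, however, is stated to record the client's own account of a self-test that was abandoned.

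**Conclusion.** The point holds in a limited form. As written, the plan gives no stated experience measure for clients who accept a kit and stop without returning a test, although it undertakes to assess participation without discomfort. If about 10% of kit recipients do not complete and are no more comfortable than completers, a completer-only comfort figure would be too high by 0 to at most 10 points. Where in that range it falls cannot be determined from the documents. The 9-point example rests on two assumptions: about 90% comfort among completers and none among non-completers. With about 20 kits only about 2 clients are affected, and the shift is small beside the sampling uncertainty.

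This does not undermine an exploratory two-pharmacy pilot that sets no acceptability threshold. It is a selection effect in a stated survey trigger that can be removed at little cost.

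**What to change.** **Section 2.4, item 8.** Offer the experience items to every client given a kit, when they leave the private area or stop, on the tablet already used there. Open with completion status (completed, started but not completed, not started) and, where relevant, the reason for stopping. State that the decline survey also covers clients who stop.

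**Section 2.11.** Use all kit recipients as the denominator for self-test feasibility and comfort. For feasibility, count non-completion as not completed. For comfort, add a worst-case sensitivity analysis that sets missing answers to not comfortable. Report the completer-only figure second.

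**Cost.** Survey skip logic, a short status-and-reason item, and a few sentences of protocol text, with no extra staff or procedure. The plan already sends survey changes to the IRB. The reported figure may be less favourable, and some clients who stop will also skip the survey, which is why the sensitivity analysis is needed.
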